## **9.2 SCREENING EVALUATIONS AND PATIENT ELIGIBILITY COMMITTEE**

All testing and assessment to determine if a patient is suitable for treatment with the HARPOON System is conducted within the standard-of care at the hospital.

## **9.3 BASELINE/PRE-PROCEDURE EVALUATIONS**

The following baseline and pre-procedure assessments, if conducted as part of the institution's standard of care, will be recorded:

- Assessment of NYHA Heart Failure Class
- 3D Transoesophageal echocardiogram (TOE)
- Assessment of Medical History

## 9.4 TREATMENT/PROCEDURE ASSESSMENTS

### 9.4.1 PROCEDURE OVERVIEW:

The HARPOON System procedure will be conducted in accordance to the HARPOON System CE-Mark Instructions for Use.

The registry investigator will be trained on device use through didactic, practicum training, and proctoring. Complete details on the preparation and use of the HARPOON System can be found in the Instructions for Use.

### 9.4.2 POST-PROCEDURE FOLLOW-UP ASSESSMENTS

**Post-procedure management:** Standard hospital protocols for the management of subjects after mitral valve surgery shall be followed.

**Discharge assessment:** All subjects shall be discharged from the hospital at the discretion of the attending cardiac surgeon. Prior to discharge, all subjects shall undergo pre-discharge testing as per hospital standard of care, which may include a comprehensive pre-discharge TTE.

**Subject follow-up:** Follow-up visits at 30 days, 1 year and annually through 5 years may be conducted in person (preferred) or via telephone interview, to minimize patient attrition, as per institution's standard of care. It is important that follow-up visit schedule be maintained as closely as possible for all subjects. Edwards recognizes that subjects may not be able to complete all scheduled follow-up at precisely the date required, and therefore, a period of time in which each visit could be completed is indicated in Table 1.

In the event that study personnel learn of a subject's hospitalization or re-operation outside the study center, the center should make every effort to obtain copies of reports or results based on tests (e.g., echocardiogram) and/or procedures performed on the study subject.

The following assessments, if conducted as part of the institution's standard of care, will be recorded through 5-year follow-up:

- Transthoracic echocardiogram (TTE)
- SAEs that results in a death, device-related events and device deficiencies/device malfunctions
- Assessment of NYHA Heart Failure Class (at 1-year follow-up only)

**Table 1** summarizes the data that will be collected at each time point, per the local standard of care.

**Table 1 - Data Collection Schedule**

	Baseline/ Pre-Procedure	Procedure	Discharge	30 Days  (+14 days)	1 Year  (+/- 30 days)	2-5 Years  (+/- 45 days)
Informed Consent	X					
Medical History	X					
TOE	X	X				
TTE 			X	X	X	X
NYHA Functional Class	X				X	
SAE that results in a death, ADE, SADE, USADE, device deficiency and device malfunction assessment 	X 	X	X	X	X	X

All follow-up dates will be calculated from the date of the implant procedure. Follow-up visits may be conducted in person (preferred) and via telephone.

Enrolled subjects for whom the implant procedure was prematurely aborted, or the HARPOON procedure was attempted but device not implanted will be followed for 30 days or until resolution of any adverse events related to the implant procedure and then exited from the registry.

TTE should be performed at 30 days, 1 year and annually through 5 year follow up or per local standard of care if TTE frequency or requirements are different from study schedule.

Safety event reporting will start at the time of enrollment, i.e. subject providing a written informed consent, through 5-year follow-up.

Only SAE that results in a death is applicable for reporting at Baseline/Pre-Procedure time point.

Abbreviations: ADE=adverse device effect; NYHA=New York Heart Association; SADE=serious adverse device effect; SAE=serious adverse event; TOE=transesophageal echocardiography; TTE=transthoracic echocardiography; USADE=unanticipated serious adverse device effect.

## 9.5 REGISTRY EXIT CRITERIA AND PROCEDURES

The reason for subject's exit from this registry will be documented on the appropriate electronic case report form (eCRF) and in the medical records for each subject.

Subjects may exit the registry for any of the following reasons:

- Device attempted but not implanted
  - Enrolled subjects for whom the implant procedure was prematurely aborted (e.g., entered operating room and anesthesia induced, but procedure not attempted) or the HARPOON procedure was attempted but device not implanted, will be followed for 30 days or until resolution of any adverse events related to the implant procedure, and then exited from the registry.
- Device Reintervention or Explant
  - Subjects who have a surgical reintervention where the device is explanted will be followed for 30 days post-reintervention or until resolution of any adverse events related to the procedure, and then exited from the registry.
- Completion per clinical investigation plan (CIP)

- Withdrawal
  - Subject Withdrawal: The subject may voluntarily withdraw from this registry at any time, without penalty or loss of benefits to which they are otherwise entitled.
  - Physician Withdrawal: The Investigator also has the right to withdraw a subject if s/he feels it is in the best interest of the subject.
  - Sponsor Withdrawal: The Sponsor may prematurely terminate the registry. Circumstances under which the Sponsor can suspend or stop this registry include, but are not limited to, low enrolment or new information regarding safety or device performance.
- Death
- Lost to follow-up
  - If a subject cannot be reached for at least two (2) consecutive follow-up visits.

For subjects who are lost-to-follow-up or withdraw early, Edwards may request the site to search death registries as available or applicable per GDPR requirements and may request the site to obtain the death certificate, if applicable.

A subject who has been withdrawn from the registry will not be replaced.

## 9.6 DEATH AND SURGICAL VALVE INTERVENTION

### 9.6.1 DEATH

In the event of subject death, every effort should be made to obtain a copy of a death summary/death certificate. Information on the cause of death will be determined by the investigator(s) and reported in the registry electronic data capture (EDC) system.

### 9.6.2 SURGICAL VALVE INTERVENTION

In the event of device explant or surgical intervention, every effort should be made to obtain a copy of the procedure notes as well as any accompanying imaging data (i.e. CT, echo). Information on the cause of explant/surgical intervention will be determined by the investigator(s) and reported in the registry EDC system. Subjects who have a surgical reintervention or whose device is explanted will be followed for 30 days or until resolution of any adverse events related to the procedure, and then exited from the registry. Effort should also be made to return any explanted devices to the Sponsor for analysis by the Edwards Complaint Handling team. Return kits for explanted devices will be provided, upon request, by the Edwards Surgical Complaint Handling Department.

## 10.0 STATISTICAL METHODS

The analysis population will consist of the subjects who were enrolled and undergone a mitral valve repair surgery with the HARPOON System, regardless of procedure outcome. The analysis population excludes any subjects who signed the registry consent but were exited from the study prior to the procedure.

There is no planned statistical hypothesis testing within this REPLICATE Registry protocol. Descriptive and summary statistical analysis will be provided for baseline/pre-procedure, procedure and outcome variables.

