## 6.2 PRIOR CLINICAL EXPERIENCE WITH THE HARPOON SYSTEM: EFS AND CE MARK TRIALS

Two (2) ongoing European clinical trials have assessed the safety and performance of the HARPOON System: the Early Feasibility Study (EFS) and the CE Marking Trial (CE Mark, conducted under two (2) clinical protocols):

The purpose of the EFS trial is to assess the safety and performance of the HARPOON System (previously the Harpoon Medical TSD-5 Device). The early data collected from the trial were used to power and support the design of the study to support CE Mark of the HARPOON System. The purpose of the CE Marking trial is to assess the safety and performance of the HARPOON System in subjects with severe degenerative mitral regurgitation by implanting ePTFE chords in the posterior leaflet of the mitral valve via transapical access thereby obviating the need for open surgery and its risks.

This clinical experience summary is based on clinical data as of 02 April 2019 for subjects enrolled from 16 February 2015 (first enrolment in EFS) to 07 November 2017 (last enrolment in CE Mark).

Sixty-five (65) subjects were enrolled at six (6) investigational sites between both studies. This includes thirteen (13) subjects enrolled in the EFS study and fifty-two (52) subjects in the CE Mark study. Of the enrolled population, sixty-two (62) subjects were implanted with the HARPOON System (thirteen (13) in the EFS trial and forty-nine (49) in the CE Mark Trial). Three patients left the operating room without the investigational device. One case was aborted before the Harpoon procedure and 2 cases were converted to standard of care (SOC) mitral valve surgery. Overall, follow-up compliance of 100% (56/56) of eligible subjects was achieved at the 1-year visit. Six (6) HARPOON System subjects were censored through 1-year including two (2) deaths and four (4) reoperations. Follow-up compliance of 98% (40/41) has been achieved so far at the 2-year visit; nine (9) subjects have yet to reach their 2-year follow-up window. Follow-up is currently ongoing.

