### **6.2.3 SECONDARY PERFORMANCE RESULTS**

#### **6.2.3.1 MITRAL REGURGITATION**

Severity of mitral regurgitation (MR) was evaluated by the Echo Core Lab at the baseline, discharge, 1-month, 6-month, 1-year, and 2-year follow-up visits for the HARPOON System cohort. At 2-year follow up, 65.8% (25/38) of patients had mitral regurgitation of mild or less, 26.3% (10/38) of patients had moderate MR and 7.9% (3/38) of patients had severe MR.

Several subjects with moderate to severe mitral regurgitation underwent re-operations and were identified as having ruptured ePTFE chords. An investigation was conducted to determine the root cause of ePTFE chord ruptures. The root cause of the chord ruptures was found to be over-tensioned chords. Findings confirmed that no material or device design changes were required. As a result of this investigation, screening and procedural updates to the IFU, Training Program Materials, and Post Market Clinical Follow-up Study were made to mitigate future ePTFE chord ruptures.

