## **7.3 OUTCOME MEASURES**

The key outcome measure is freedom from re-operation due to recurrent severe mitral regurgitation through 1-year post-implant.

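### Does Section 10.0 leave the one-year freedom-from-re-operation figure undefined for patients in whom the device was attempted but not implanted?

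*Combined protocol and SAP*

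**What the plan says.** The analysis population in Section 10.0 is "subjects who were enrolled and undergone a mitral valve repair surgery with the HARPOON System, regardless of procedure outcome". A second sentence there removes patients who consented but left before the procedure. The analysis is descriptive, covers baseline, procedure and outcome variables, and includes no hypothesis test.

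The one named outcome, in Section 7.3 and the synopsis, is "freedom from re-operation due to recurrent severe mitral regurgitation through 1-year post-implant". Table 1, footnote 1, dates all follow-up from the implant procedure. Section 7.4 sets the target at about 150 implanted patients, of whom up to 30 may join after their surgery.

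Under Section 9.5, patients in whom "the HARPOON procedure was attempted but device not implanted, will be followed for 30 days or until resolution of any adverse events" linked to the procedure then leave the registry; Table 1, footnote 2, says the same. The same heading covers cases stopped earlier, described as "entered operating room and anesthesia induced, but procedure not attempted". Section 9.5 also requires the reason for exit to be recorded on an eCRF.

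**The concern.** The population is defined by surgery and the outcome by implant. An attempted but non-implanted patient falls between the two: included in the analysis set, without an implant, and usually gone long before one year. No estimator, censoring rule or outcome-specific denominator is given, so two analysts could print different denominators for the registry's only named outcome.

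Under each of the three natural readings, a patient converted to open mitral surgery during the index operation never counts against the device. If conversions were common, the headline percentage could look reassuring while an important kind of technical failure stayed out of view. Cases stopped after anaesthesia also look unplaced at first: they have not had HARPOON surgery, but neither have they left the registry before the day of the procedure.

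**Working it through.** **Inputs (Sections 6.2 and 6.2.1).** The two earlier trials enrolled 13 + 52 = 65 patients and implanted 13 + 49 = 62. Of the other three, "One case was aborted before the Harpoon procedure and 2 cases were converted to standard of care (SOC) mitral valve surgery", so 65 − 1 = 64 were attempted. For the first year the protocol reports: "Six (6) HARPOON System subjects were censored through 1-year including two (2) deaths and four (4) reoperations". This agrees with the 56 patients eligible at one year (62 − 6 = 56). One re-operation is described as early.

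REPLICATE states no target rate or precision, so there is no plan figure to reproduce.

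**Assumptions.** All four re-operations count as events, although Section 6.2 does not give their cause. The two deaths are not failures and stay in the denominator. The early re-operation fell before day 30.

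**The three readings** (exact Clopper-Pearson 95% intervals):

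| Handling of the 2 converted patients | Calculation | Freedom at 1 year |
|---|---|---|
| Counted as free | (64 − 4)/64 = 60/64 | 93.8% (84.8 to 98.3) |
| Censored at day 30 | (63/64) × (58/61) | 93.6% |
| Left out | (62 − 4)/62 = 58/62 | 93.5% (84.3 to 98.2) |

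In the censored row, 64 are at risk and 1 fails before day 30. The 2 converted patients then leave, so 64 − 1 − 2 = 61 remain, and 3 of them fail. The spread is 93.75 − 93.55 = 0.2 points.

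**The aborted case.** Adding it as free gives 61/65 = 93.8%, which is 0.1 point above 60/64. Section 10.0 in any case requires that surgery with the system took place, and a case in which the procedure was not attempted does not meet that.

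**Conversion as a failure.** (64 − 4 − 2)/64 = 58/64 = 90.6% (80.7 to 96.5), about 3 points lower.

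**Projection to the registry.** Suppose 30 of the 150 join already implanted, leaving 120 prospective implants, and the prior rates carry over.

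- Expected conversions: 120 × 2/62 = 3.9. The 95% predictive range is 0 to 15, using a Beta(2.5, 62.5) rate and a negative binomial count.
- Expected re-operations: 120 × 4/62 = 7.74.
- Left out: 1 − 7.74/120 = 93.5%.
- Counted as free: 1 − 7.74/124 = 93.8% with 4 conversions, and 1 − 7.74/135 = 94.3% with 15.
- Counted as failures: 1 − (7.74 + 4)/124 = 90.5% with 4 conversions, and 1 − (7.74 + 15)/135 = 83.2% with 15.

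The choice of reading is therefore worth about 0.2 points, and about 0.7 at the upper limit. For scale, 140/150 = 93.3% has an exact 95% interval of 88.1% to 96.8%.

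**The case for a change.** The strongest case for a change does not depend on the 0.2 points. It is that technical failure at the index operation has no stated place beside the durability figure. In the earlier trials, procedural success required leaving the operating room with at least one chord in place and was reported on everyone enrolled (Section 6.2.2: 11/13 and 46/52), so a non-implant counted against the device. REPLICATE names no such measure. Section 11.1 limits event reporting to device-related effects, deaths and deficiencies. Conversion is listed only in Attachment A, whose definitions are suggested rather than required, and only among device-related events as judged by the investigator. Being descriptive is no full defence either, since a registry's main product is this percentage.

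Part of this stands. No sentence commits the sponsor to reporting conversions, or to separating them from aborted cases.

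The rest is weaker than it looks:

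- The limit in Section 11.1 applies to safety events, not to procedure or exit forms.
- Section 9.5 has the exit reason recorded on an eCRF and names non-implantation as a category.
- Section 9.6.2 sends the cause of any surgical intervention to the EDC system.
- Section 10.0 plans summaries of procedure variables in a population kept whatever the procedure outcome.
- Time zero is given in Table 1.

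That a conversion is never a failure follows from the choice of outcome. Surgery at the index operation is neither a re-operation nor a response to recurrent regurgitation. Counting it would create a composite of technical failure and durability, on which reasonable statisticians differ.

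**Conclusion.** No change follows. The plan is silent on the estimator and on the denominator for attempted but non-implanted patients. The outcome's own wording and the implanted-patient target both point an analyst to implanted patients, with time running from the implant procedure. The other readings move the result by about 0.2 points on prior counts and about 0.7 at the upper limit of the projection, well inside the sampling uncertainty. No test, error rate or power calculation depends on the choice.

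The 3-point difference, with a projected range of 0 to 10 points, answers a different question because it redefines the outcome. It rests on 2 conversions in 64 attempts (3.1%, exact 95% interval 0.4 to 10.8), on re-operations whose cause is not given, and on rates that may no longer apply, because after the chord-rupture investigation "screening and procedural updates to the IFU, Training Program Materials, and Post Market Clinical Follow-up Study were made" (Section 6.2.3.1).

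The conclusion assumes that the report will give the denominator it uses and that the planned exit and procedure summaries will show the non-implanted cases. It would be less secure if conversions proved far more frequent than before and those summaries did not show them.

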## 11.0 SAFETY REPORTING

Safety event reporting to the sponsor is the Investigator's responsibility and will start at the time of enrolment and will continue through the duration of the registry.

The following critical safety events will be collected in this registry:

- SAEs where the outcome is death, and
- Device-related events/deficiencies.

These events will be recorded in the EDC system by the Clinical Study Coordinator (or designated site personnel). If the EDC system is not accessible, the event should be reported to the sponsor by using the following e-mail address: [[contact]](mailto:[contact]). Note: the event(s) will still need to be recorded in the EDC once the system is functional.

All the information related to the reported events, such as an awareness date, start and stop dates, description of event, seriousness, action taken and outcome, and relatedness to the HARPOON System procedure and device, will be assessed and recorded in the EDC system in a timely manner by the site. Whether an event meets the definition of serious or device-related will be determined by the registry investigator using the ISO 14155 definitions (see **Table 2**). Relatedness of the event to the HARPOON System device will be determined by the investigator by using the causality categories listed below.

All relevant source documentation for reported events should be forwarded to Sponsor Safety Department via email [[contact]](mailto:[contact]). Source documentation must be redacted to remove identifiable references to the patient prior to submission to Sponsor.

Sponsor's Surgical Safety Team will review all reported events as per applicable regulatory requirements and Sponsor's internal standard operating procedures, including vigilance assessment and reporting to Edwards Complaint Handling or Regulatory Affairs groups who performs appropriate reporting to Regulatory Authorities, if applicable and per national legislation.

Local safety reporting to ethics committees will be completed, as required. Events will be collected and reported through 5 years post-procedure.

### 11.1 DEFINITIONS OF DEVICE-RELATED ADVERSE EVENTS AND DEVICE DEFICIENCIES

Table 3 below includes all event definitions as per ISO14155. Please note that for this registry, only the following events will be reported on the eCRFs:

- Adverse device effect (ADE)
- Serious adverse device effect (SADE)
- Unanticipated serious adverse device effect (USADE)
- SAE that results in a death
- Device deficiency/device malfunction

**Table 2: Adverse Event Definitions (ISO 14155)**

Term	Definition
Adverse event (AE)	
Any untoward medical occurrence, unintended disease or injury, or untoward clinical signs (including abnormal laboratory findings) in subjects, users or other persons, whether or not related to the investigational medical device
 
NOTE 1: This definition includes events related to the investigational medical device or the comparator.
 
NOTE 2: This definition includes events related to the procedures involved.
 
NOTE 3: For users or other persons, this definition is restricted to events related to investigational medical devices.

Serious adverse event (SAE)	
An adverse event that:
 

• led to a death,

• led to serious deterioration in the health of the subject, that either resulted in

• a life-threatening illness or injury, or

• a permanent impairment of a body structure or a body function, or

• in-subject or prolonged hospitalization, or

• medical or surgical intervention to prevent life-threatening illness or injury or permanent impairment to a body structure or a body function,

• led to fetal distress, fetal death or a congenital abnormality or birth defect

 
NOTE: Planned hospitalization for a pre-existing condition, or a procedure required by the CIP, without serious deterioration in health, is not considered a serious adverse event.

Adverse device effect (ADE)	
Adverse event related to the use of an investigational medical device
 
NOTE 1: This definition includes adverse events resulting from insufficient or inadequate instructions for use, deployment, implantation, installation, or operation, or any malfunction of the investigational medical device.
 
NOTE 2: This definition includes any event resulting from use error or from intentional misuse of the investigational medical device

Serious adverse device effect (SADE)	Adverse device effect that has resulted in any of the consequences characteristic of a serious adverse event above.
Unanticipated serious adverse device effect (USADE)	Serious adverse device effect which by its nature, incidence, severity or outcome has not been identified in the current version of the risk analysis report.

Term	Definition
	NOTE: Anticipated serious adverse device effect (ASADE) is an effect which by its nature, incidence, severity or outcome has been identified in the risk analysis report.
Device deficiency	Inadequacy of an investigational medical device related to its identity, quality, durability, reliability, safety or performance. This may include malfunctions, use error, or inadequacy in the information supplied by the manufacturer.
Device malfunction	Failure of an investigational medical device to perform in accordance with its intended purpose when used in accordance with the instructions for use (IFU) or CIP.
Use Error	Act or omission of an act that results in a different medical device response than intended by the manufacturer or expected by the user  NOTE 1: Use error includes slips, lapses, and mistakes.  NOTE 2: An unexpected physiological response of the subject does not in itself constitute a use error.

